7.1 AutoHSCT Analysis Set

Includes all subjects who achieve a response **per investigator's review** and undergo autoHSCT **while in remission and without any other anti-cancer treatment**.

7.2 AlloHSCT Analysis Set

Includes all subjects who achieve a response per investigator's review and undergo alloHSCT while in remission and without any other anti-cancer treatment.

7.3 Full Analysis Set (FAS)

The FAS includes all subjects who are treated with blinatumomab.

7.4 Target Dose Analysis Set (TDAS)

All subjects of the FAS who completed at least seven days of infusion on the highest intended dose level will constitute Target Dose Analysis Set (TDAS). In addition, all subjects who discontinue the treatment during the first cycle of treatment due to

progression of disease **per end of treatment reason on CRF** will be included. Primary efficacy endpoint will be analyzed using TDAS.

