8.3 Reasons for Removal From Treatment, or Study

8.3.1 Reasons for Removal From Treatment

Reasons for removal from protocol-required IP(s) or procedural assessments include any of the following:

- subject request
- safety concern (eg, due to an adverse event, ineligibility determined, protocol deviation, non-compliance, protocol-specified criteria, pregnancy)
- death
- lost to follow-up
- decision by sponsor (other than subject request, safety concern, lost to follow-up)
- disease progression

Subjects who discontinue treatment will continue to be followed on the study.

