9. SAFETY DATA COLLECTION, RECORDING, AND REPORTING

9.1 Definition of Safety Events

9.1.1 Disease Related Events

Disease Related Events are events (serious or non-serious) anticipated to occur in the study population due to the underlying disease, **eg, disease progression**. Such events do not meet the definition of an adverse event unless assessed to be more severe than expected for the subject's condition.

Disease Related Events that do not qualify as Adverse Events or Serious Adverse Events:

- An event which is part of the normal course of disease under study (eg, disease progression in oncology or hospitalization due to disease progression) is to be reported as a Disease Related Event.
- Death due to the disease under study is to be recorded on the Event CRF.

Approved

Disease Related Events that would qualify as an Adverse Event or Serious Adverse Event:

- An event based on the underlying disease that is worse than expected as assessed by the investigator for the subject's condition or if the investigator believes there is a causal relationship between the IP(s)/study treatment/protocol-required therapies and disease worsening, this must be reported as an Adverse Event or Serious Adverse Event.

Table 11. outlines the expected Disease-Related Events by System Organ Class.

Table 11. Disease-related Adverse Events by System Organ Class

SOC	Preferred Terms
Investigations	weight decreased
Blood and lymphatic system disorders	lymphadenopathy
General disorders and administration site conditions	disease progression fatigue
Skin and subcutaneous tissue disorders	night sweats
Other	hemorrhage ^c disease progression

SOC = system organ class.

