10.1.2.3 Target Dose Analysis Set (TDAS)

All subjects of the FAS who completed at least 7 days of infusion on the highest intended dose level will constitute Target Dose Analysis set (TDAS). In addition, all subjects who discontinue the treatment due to progression of disease during the first cycle of treatment will be included. The primary efficacy endpoint will be analyzed using TDAS.

Approved

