10.2 Sample Size Considerations

10.2.1 Phase 2

The sample size for the phase 2 part of the study is determined by a 1-sample test of the rate of CMR **during the first 12 weeks** after **initiation** of blinatumomab. With the 1-sided type I error rate (α) set at 0.025, a null hypothesis response probability (π_0) of 15%, and an alternative response probability (π_1) of 40%, a sample size of 36 subjects will provide 90% power to reject the null hypothesis that the response probability is no more than 15%. Being able to make this determination will represent evidence of clinical activity and warrant advancement into the phase 3 part of the study.

10.2.2 Phase 3

The primary endpoint is CMR. A CMR rate of 22% in the IC arm vs. 40% in the blinatumomab arm is hypothesized. The odds ratio of CMR rate will be tested at the 1-sided significance level of 0.025. With these assumptions and a 1:1 randomization

ratio, a sample size of 296 subjects will provide 89% power. The sample size is adjusted for 3 interim futility analyses when 25%, 50%, and 75% of the subjects have had the opportunity to complete the tumor assessment and 1 interim efficacy analysis when 75% of the subjects have had the opportunity to complete the tumor assessment. The interim futility boundaries will use a Lan-DeMets beta-spending approach to an O'Brien-Fleming boundary and the interim efficacy boundaries will use a Lan-DeMets alpha-spending approach to an O'Brien-Fleming boundary. The details of these interim analyses are specified in the [Section 10.4.1](#).

Overall survival is a key secondary endpoint and the study is also powered for overall survival. If the null hypothesis for the primary endpoint is rejected, then OS will also be tested at a 1-sided significance level of 0.025. Assuming the true hazard ratio is 0.65 a final OS analysis after 236 death events will provide 90% power. With a median survival time of 4.4 months in the IC arm vs. 6.7 months in blinatumomab arm, accrual rates of 14.5 subjects per month, a 5% drop-out rate per year, and a targeted sample size of 296 randomized subjects, it is estimated that the 236th event will occur within 26 months of the start of randomization.

Sample size re-estimation will be allowed at an interim analysis (see [Section 10.4.1](#)).

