10.5.1 Analyses of Primary Efficacy Endpoint

The percentage of subjects with a CMR by central review during the 12 weeks after initiation of blinatumomab will be summarized with an exact binomial 95% confidence interval using FAS. A summary of CMR during the treatment will also be provided using TDAS.

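### The TDAS keeps early progressors only by the end-of-treatment reason on the CRF, so an early lymphoma death coded as death can drop out of the denominator and raise the TDAS CMR rate slightly

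*SAP*

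**What the plan says.** SAP 7.4 gives two routes into the TDAS. The main route is for FAS subjects who "completed at least seven days of infusion on the highest intended dose level". The second is for subjects who stop in Cycle 1 because of progression, identified "per end of treatment reason on CRF". Protocol 10.1.2.3 has the same second route without naming a data field: "all subjects who discontinue the treatment due to progression of disease during the first cycle of treatment will be included". SAP section 11, which lists changes from the protocol, does not mention the added condition.

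Protocol 8.3.1 opens its list with "Reasons for removal from protocol-required IP(s) or procedural assessments include any of the following". Death and disease progression are separate entries in that list. Protocol 9.1.1 says: "Death due to the disease under study is to be recorded on the Event CRF". Neither document links that entry to the end-of-treatment reason.

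On the use of the set, SAP 7.4 states "Primary efficacy endpoint will be analyzed using TDAS". SAP 10.5.1 puts the 12-week CMR rate, with its exact 95% interval, on the FAS and then adds "A summary of CMR during the treatment will also be provided using TDAS".

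**The concern.** The second route keeps patients whose disease failed early in the denominator even though they never had a week at target dose. Tying it to one CRF field makes membership depend on how the end of treatment was entered. Take two subjects with rapidly progressing lymphoma in week 2. One is taken off treatment for progression and stays in the TDAS. The other dies a day later while still on treatment, has death entered as the reason, and is left out. The second had the worse outcome.

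The direction of the effect is fixed. The scheduled response scan is at about day 70, and SAP 9.3 counts a subject with no post-baseline assessment as not having achieved CMR. Leaving out an early lymphoma death lowers the denominator and does not change the numerator. With at least one CMR in the set, the TDAS rate can only go up. It would then partly reflect who survived long enough to reach target dose.

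**Working it through.** **The plan's own figure.** SAP 3.2 gives 36 subjects, a 15% null, a 40% alternative, one-sided alpha 0.025 and 90% power. With an exact binomial test that rejects at 11 or more CMRs, P(X >= 11 | 36, 0.15) = 0.0137 and P(X >= 11 | 36, 0.40) = 0.910. Rejecting at 10 or more would give alpha 0.035. The stated sample size and power are reproduced.

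**The window.** Target dose starts on day 15 (protocol 6.2.1), so seven days at target are complete at about day 21 at the earliest. An interruption with stepwise re-escalation (protocol 6.2.2.2) would move this later.

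**The effect of leaving out k subjects.** With x CMRs among 36 treated subjects and k early lymphoma deaths left out, the rate goes from x/36 to x/(36-k), a factor of 36/(36-k). The last two columns show 0.40 and 0.15 multiplied by that factor.

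| k | Factor | 10 CMRs | 14 CMRs | FAS rate 40% becomes | FAS rate 15% becomes |
|---|---|---|---|---|---|
| 0 | 1.000 | 27.8% | 38.9% | 40.0% | 15.0% |
| 1 | 1.029 | 28.6% | 40.0% | 41.1% | 15.4% |
| 2 | 1.059 | 29.4% | 41.2% | 42.4% | 15.9% |
| 3 | 1.091 | 30.3% | 42.4% | 43.6% | 16.4% |
| 4 | 1.125 | 31.3% | 43.8% | 45.0% | 16.9% |

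Per subject this is about 0.4 to 0.5 points at 15% and 1.1 to 1.4 points at 40%. The factor assumes that nobody else is excluded. If the correctly defined TDAS had m subjects, the factor would be m/(m-k). With m = 30 and k = 1, for example, it is 30/29 = 1.034 rather than 1.029.

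**How many such deaths.** The documents give no early-death rate for this population. For scale only, take the phase 3 planning assumption in protocol 10.2.2, "With a median survival time of 4.4 months in the IC arm vs. 6.7 months in blinatumomab arm", and assume exponential survival:

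- P(death by day 21) = 1 - 2^(-(21/30.44)/median).
- Median 4.4 months: 10.3%, and 36 x 0.103 = 3.7 subjects.
- Median 6.7 months: 6.9%, and 36 x 0.069 = 2.5 subjects.

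These are deaths from any cause. Only those from lymphoma, not already stopped for progression, and coded as death would be lost from the TDAS.

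**The comparison with 15%.** Exact (Clopper-Pearson) 95% lower limits were computed for 8 to 13 CMRs with 0 to 4 subjects left out. With 9 CMRs the limit stays below 15% even at 9/32 (13.7%). With 11 it is already above at 11/36 (16.3%). It crosses 15% only at exactly 10 CMRs: 14.2% at 10/36, 14.6% at 10/35, 15.1% at 10/34. The probability of exactly 10 CMRs among 36 is 4.5% at a true rate of 40%, about 14% at 25 to 30%, and 2.1% at 15%.

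**The case against.** The strongest reply is that the main result is safe. Protocol 10.1.2 puts the phase 2 primary efficacy analysis on all subjects who received blinatumomab, and SAP 10.5.1 reports the 12-week CMR rate on the FAS, where an early death with no assessment counts against the drug. This stands, and it limits the point to the TDAS.

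The coding is also an inference. The CRF and its completion guidelines are not among the documents, and protocol 8.3.1 gives no order of precedence between death and progression. Subjects are examined at least weekly, so many failing patients would be stopped for progression before they died. Entry requires ECOG 0 to 2, adequate laboratory values and an intention to transplant, so there may be no cases at all. This stands too: the claim is that such a subject can be coded as a death, not that one will be.

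The protocol's exception does not mention deaths either, and the TDAS leaves out early stops for toxicity by design. That is fair. However, an exception written for disease progression that can miss the patients whose disease killed them is a different matter from the intended selection on dose. Discontinuation reasons are tabulated and deaths are listed (SAP 10.2 and 10.6.1), so a careful reader could spot such cases, but the reported rate would not be corrected.

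A reader might also infer that leaving out two early deaths is enough to turn a result that does not exclude 15% into one that does. The documents do not support that as a general statement. It happens only at exactly 10 CMRs. SAP section 5 describes the CMR rate as something to be estimated, the 15% null appears only in the sample-size text, and no test on the TDAS is planned.

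**Conclusion.** The gap is real and small. As worded, SAP 7.4 allows an early lymphoma death coded as a death to drop out of the TDAS, and each such exclusion raises the TDAS CMR rate by roughly 1 percentage point. This rests on two assumptions: that the end-of-treatment page follows the list in protocol 8.3.1, and that at least one such death occurs. The figure of 2.5 to 3.7 is best read as a generous guide to scale: it counts deaths from every cause, relies on phase 3 planning medians and an exponential curve, and uses the earliest possible day of completion. Zero cases remains plausible.

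The analyses affected are those on the TDAS: the primary endpoint on that set according to SAP 7.4, and CMR during treatment according to SAP 10.5.1. It would be wrong to conclude that the trial's main CMR estimate is biased; that estimate is on the FAS and does not change. This is a cheap improvement.

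**What to change.** Change the second route in SAP 7.4 to read along these lines: *In addition, FAS subjects who stop treatment in Cycle 1 because of progression, or who die in Cycle 1 with lymphoma as the reported cause of death, are included, whatever the end-of-treatment reason on the CRF.*

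No new data are needed. Cause of death is collected under protocol 7.3.17, and lymphoma deaths go on the Event CRF under protocol 9.1.1. The cost is one sentence in the SAP and one more condition in the population flag. The downside is that the TDAS rate becomes slightly less favourable if any such death occurs; if none does, nothing changes. A listing of FAS subjects left out of the TDAS, with the reason for each, would let readers check the result.

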10.1.2 Analysis Sets

The primary analysis of efficacy from **the phase 2 part of the study will be performed on all subjects who received blinatumomab. The primary analysis of efficacy from the phase 3 part of the study will be performed on all randomized subjects analyzed according to their randomized treatment assignment (the Full Analysis Set [FAS]).**

Sensitivity analyses of efficacy will be performed on the Safety Analysis Set.

The primary analysis of safety will be performed on the Safety Analysis Set which will include all subjects who received protocol-specified therapy analyzed according to the treatment they received.

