10.4.3 Primary Analysis

Phase 2: The primary analysis will report the CMR rate among blinatumomab treated subjects.

Phase 3: The primary analysis will test whether CMR/OS is superior in the group randomized to blinatumomab compared to the group randomized to IC. The primary analysis will be triggered by the date when 296 subjects have had the opportunity to

complete at least 1 tumor assessment. Barring a sample-size increase, the estimated time of this analysis is 21 months after the first subject is randomized.

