3.2 Sample Size

The sample size for the study is determined by a one-sample test of the rate of CMR during first 12 weeks after initiation of blinatumomab. With the one-sided type I error rate (α) set at 0.025, a null hypothesis response probability (π_0) of 15%, and an alternative response probability (π_1) of 40%, a sample size of 36 subjects will provide 90% power to reject the null hypothesis that the response probability is no more than 15%.

4. Study Endpoints and Covariates

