4.2 Exploratory

- To characterize the pharmacodynamic effects of blinatumomab administered in temporal proximity to various S1 regimens
- To evaluate the response rate according to disease-specific features, such as cell-of-origin (COO), c-myc and bcl-2 rearrangements **and over expression, Revised International Prognostic Index (R-IPI), Secondary International Prognostic Index (IPI), National Comprehensive Cancer Network International Prognostic Index (NCCN IPI), first response status before blinatumomab, duration of first remission before blinatumomab**
- To evaluate the frequency of **tumor-associated mutations in cell-free (CF) circulating tumor (CT- DNA)** among subjects at various time points during and after salvage treatment
- To determine the incidence of anti-blinatumomab antibody formation

5. Hypotheses and/or Estimations

The complete metabolic response (CMR) rate during the first 12 weeks since starting blinatumomab will be estimated for blinatumomab monotherapy administered in the second salvage (S2) treatment of transplant-eligible subjects with relapsed or refractory (R/R) aggressive B-NHL who have not achieved CMR.

6. Definitions

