10.5 Efficacy Analyses

Efficacy analyses will be performed on the FAS unless specified otherwise.

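### The plan puts the primary CMR endpoint on the Target Dose Analysis Set in one place and on all treated subjects in others, without ranking the two

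*SAP*

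**What the plan says.** Two passages point to TDAS. SAP 7.4 says "Primary efficacy endpoint will be analyzed using TDAS", and protocol 10.1.2.3 says "The primary efficacy endpoint will be analyzed using TDAS". TDAS contains FAS subjects with at least seven days of infusion at the highest intended dose level, plus those who discontinue in the first cycle because of progression.

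Other passages point to all treated subjects:

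- Protocol 10.1.2: the primary efficacy analysis from "the phase 2 part of the study will be performed on all subjects who received blinatumomab".
- Protocol 10.4.3: "The primary analysis will report the CMR rate among blinatumomab treated subjects".
- SAP 10.5.1: the 12-week central-review CMR rate is reported on the FAS with an exact interval, and TDAS is used for an additional summary of CMR over the treatment period.
- SAP 10.5: "Efficacy analyses will be performed on the FAS unless specified otherwise".

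SAP 7.3 defines the FAS as all subjects treated with blinatumomab. SAP section 5 frames the objective as estimation: "The complete metabolic response (CMR) rate during the first 12 weeks since starting blinatumomab will be estimated for blinatumomab monotherapy". The comparison with 15% appears only in the sample-size text. SAP 3.2 says that "a sample size of 36 subjects will provide 90% power to reject the null hypothesis that the response probability is no more than 15" per cent, and protocol 10.2.1 adds that rejecting this null would warrant moving to phase 3.

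**The concern.** An unqualified statement that the primary endpoint is analyzed on TDAS sits beside a primary analysis on the FAS, and nothing ranks them. The SAP 10.5 default to the FAS yields wherever another set is specified, and SAP 7.4 specifies one. The TDAS sentence in SAP 10.5.1 concerns CMR during treatment, not the 12-week endpoint, so the analysis that 7.4 calls for has no planned method. The only set that the protocol names for sensitivity analyses of efficacy is the Safety Analysis Set, which SAP 7.6 says equals the FAS. SAP section 11 covers only who reviews the scans. Amendment 2 introduced both the all-treated sentence and TDAS, so neither supersedes the other.

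TDAS membership depends on what happens after treatment starts. Subjects who stop early for toxicity leave the denominator. Some may still be scanned 14 (+3) days after the last dose (protocol Table 6, footnote q) and could be in CMR. Those with no post-baseline assessment count as non-CMR in the FAS (SAP 9.3) but disappear from TDAS. If the omitted subjects respond less often than the rest, the TDAS rate is too high. In an open-label single-arm study, an unresolved denominator also leaves room to choose it after the results are known.

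**Working it through.** **The plan's own figure.** Inputs from SAP 3.2: n = 36, null rate 15%, alternative 40%, one-sided alpha 0.025. With an exact binomial test, the smallest r with P(X ≥ r | 36, 0.15) ≤ 0.025 is r = 11. The exact alpha is 0.0137 and the power at 40% is 0.910, which matches the stated 90%.

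**Effect on one result.** Exact (Clopper-Pearson) lower 95% limits:

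| Result | Rate | Lower limit | One-sided p against 15% |
|---|---|---|---|
| 10/36 (FAS) | 27.8% | 14.2% | 0.035 |
| 10/34 (two excluded, neither a CMR) | 29.4% | 15.1% | 0.024 |
| 9/34 (two excluded, one a CMR) | 26.5% | 12.9% | 0.059 |

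The second row changes the reading against 15%. The third does not.

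**Plausible number of exclusions.** The documents give none, so I assume 0 to 6. The nearest figure is the earlier phase 2 study in protocol 2.2: 25 subjects (23 on stepwise dosing), ORR 43% and CR 19% among evaluable subjects. The only denominator up to 25 that rounds to both percentages is 21 (9/21 and 4/21). That leaves out 4 of 25, or 2 of 23 if only stepwise dosing counts. Scaled to 36, this is 36 × 4/25 = 5.8 or 36 × 2/23 = 3.1. Protocol 2.2 does not define evaluable, and it is not TDAS, so this is only a rough anchor.

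**Chance of crossing 15% on TDAS when the true all-treated rate is 15%.** Let k subjects be excluded, with CMR rate q. The remaining 36 − k then have rate p = (0.15 × 36 − kq)/(36 − k), and the chance is P(X ≥ r | 36 − k, p). The critical count r is 11 for 35 or 36 subjects and 10 for 30 to 34. For example, k = 2 and q = 0 give p = 5.4/34 = 0.159 and P(X ≥ 10 | 34, 0.159) = 0.0343.

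| Excluded, k | q = 0 | q = 5% | q = 10% | q = 15% |
|---|---|---|---|---|
| 1 | 0.0135 | 0.0126 | 0.0118 | 0.0110 |
| 2 | 0.0343 | 0.0306 | 0.0271 | 0.0240 |
| 3 | 0.0339 | 0.0284 | 0.0236 | 0.0195 |
| 4 | 0.0334 | 0.0263 | 0.0205 | 0.0156 |
| 5 | 0.0329 | 0.0243 | 0.0176 | 0.0124 |
| 6 | 0.0323 | 0.0224 | 0.0150 | 0.0097 |

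The FAS rule (at least 11 of 36) has 0.0137. Nine of the 24 cells exceed 0.025, and the largest is 0.034. Part of the rise is discreteness: at k = 2 and q = 15%, where there is no selection, the chance is already 0.024 because the critical count drops from 11 to 10.

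**The case against.** The strongest reply is that the primary set is not really in doubt. Protocol 10.1.2 and 10.4.3 use the words primary analysis and refer to treated subjects. SAP 10.5.1 is headed as the analysis of the primary endpoint and uses the FAS. The TDAS sentences say neither primary analysis nor only, and an endpoint can be analyzed on two sets; SAP 6.2 defines the CMR rate relative to the respective analysis set. I accept that the FAS is the likely intent and that this is ambiguity more than flat contradiction. It does not settle the matter, because the supplementary role that SAP 10.5.1 gives TDAS is for a different summary.

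The size is also open to challenge, and these points stand. Exclusion counts are assumed, 15 of the 24 scenarios stay at or below 0.025, and no passage prescribes a test of 15% on TDAS. TDAS keeps first-cycle discontinuations for progression, so those failures remain in the denominator. If no excluded subject is a CMR and at most six are excluded, the reading against 15% changes only at exactly 10 CMRs with at least two excluded; P(X = 10 | 36, 0.15) is 0.021.

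A further argument is that section 11 has nothing to record, because the TDAS sentence is the same in both documents. That is true today. Once SAP 7.4 is corrected it will differ from protocol 10.1.2.3, and the note becomes appropriate.

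**Conclusion.** The concern holds and should be fixed. Both documents contain a rule that, if followed, bases the primary CMR rate on a set selected by events after treatment starts, while other passages use all treated subjects. Confidence in the textual conflict is high. The numerical effect is modest and conditional: with two to six exclusions and no CMR among them, the chance of wrongly crossing 15% is 0.032 to 0.034 against 0.014 on the FAS. With one exclusion, or with excluded subjects responding at 15%, it does not exceed 0.025. These figures assume 36 treated subjects and a comparison with 15% that comes only from the sample-size text. The sample size and its power are unaffected.

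**What to change.** - In SAP 7.4, citing protocol 10.1.2, state that the primary analysis of 12-week central-review CMR, and any comparison with 15%, uses the FAS. Label TDAS supplementary.
- In SAP 10.5.1, add the same 12-week CMR on TDAS, with the number of subjects excluded and the reason and CMR status of each.
- Note the difference from protocol 10.1.2.3 in SAP section 11, and correct that protocol sentence at the next amendment.

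The cost now is a sentence in 7.4, the matching edits to 10.5.1 and section 11, and one relabelled table. The protocol sentence needs an amendment with IRB/IEC approval (protocol 12.1), so it can wait for the next one. The highlighted CMR rate may be lower than it would be on TDAS.
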